8.3.2 HCV Days 60-210, Visits H02-H07

Visit	Target (Day)	Window (Days)
H02	60	± 7
H03	90	± 7
H04	120	± 7
H05	150	± 7
H06	180	± 21
H07	210	± 7

• Counseling and written information on acute hepatitis C treatment options will be provided along with a list of healthcare providers who are separate from this study; a referral to a community-based healthcare provider will be offered.

- Counseling on avoidance of HCV transmission, HIV infection, and pregnancy will be conducted.
- Referral to drug treatment and needle exchange programs will be provided.
- Current health status will be reviewed and any changes since the last visit will be noted.
- A targeted physical examination may be performed, if indicated, based on review of the current health status.
- Behavioral risk will be assessed using an interviewer administered questionnaire, if applicable.
- SAEs that have occurred since the last contact will be collected.
- Approximately 133 mL of venous blood for hematology, biochemistry, HCV genotyping, HCV quantitative viremia, and immunology will be collected.

8.3.3 HCV Day 240, Visit H08

(Window: HCV Day 233 to 247)

- Counseling and written information on acute hepatitis C treatment options will be provided along with a list of healthcare providers who are separate from this study; a referral to a community-based healthcare provider will be offered.
- Counseling on avoidance of HCV transmission, HIV infection, and pregnancy will be conducted.
- Referral to drug treatment and needle exchange programs will be provided.
- Current health status will be reviewed and any changes since the last visit will be noted.
- A targeted physical examination may be performed, if indicated, based on review of the current health status.
- Behavioral risk will be assessed using an interviewer administered questionnaire, if applicable.
- SAEs that have occurred since the last contact will be collected.
- Approximately 33 mL of venous blood for hematology, biochemistry, HCV genotyping, and HCV quantitative viremia will be collected.

8.3.4 HCV Day 270, Visit H09

(Window: HCV Day 263 to 277)

- Counseling and written information on acute hepatitis C treatment options will be provided along with a list of healthcare providers who are separate from this study; a referral to a community-based healthcare provider will be offered.
- Counseling on avoidance of HCV transmission, HIV infection, and pregnancy will be conducted.
- Referral to drug treatment and needle exchange programs will be provided.
- Current health status will be reviewed and any changes since the last visit will be noted.
- A targeted physical examination may be performed, if indicated, based on review of the current health status.
- Behavioral risk will be assessed using an interviewer administered questionnaire.
- SAEs that have occurred since the last contact will be collected.
- Approximately 143 mL of venous blood for hematology, biochemistry, HCV genotyping, anti-HCV, HbsAg, anti-HIV, HCV quantitative viremia, and immunology will be collected.
- Subjects will be thanked for participating in the study and contact information for end of study results will be confirmed.

8.4 Unscheduled Visit(s)

Unscheduled visits may occur at any time during the study. They may occur for the following reasons:

- (1) For operational reasons, e.g., a subject may request to reschedule, or to ask questions;
- (2) For AE related reasons. When interim contacts or visits are completed in response to subject reports of AEs, study staff will assess the reported event clinically and provide or refer the subject to appropriate medical care. All AEs will be evaluated and reported as required (Section 9.3);
- (3) If a subject presents to the study site after having missed a scheduled visit (e.g., in response to locator/tracing efforts) on a day that does not fall within a scheduled visit window;
- (4) For other reasons at subject request. All interim contacts and visits will be documented in subjects' study records and on applicable data collection forms.

8.5 Early Termination

Subjects may voluntarily withdraw their consent for participation in the study at any time and for any reason, without penalty. Subjects may also withdraw voluntarily from receiving the study intervention for any reason. A site principal investigator may also withdraw a subject from receiving further study intervention. Follow-up safety assessments and immunogenicity evaluations will be completed, if possible, whether the subject withdraws from the study or is withdrawn from receiving further study product. Subjects will be encouraged to permit continued follow-up of AE/SAEs and to donate scheduled venous blood samples for clinical safety laboratory and immunogenicity evaluations, if possible – see the protocol-specific MOP for alternate follow-up requirements. For subjects who withdraw within 180 days of their last dose of vaccine, a 6-month follow-up phone call should be conducted to collect any new SAEs.

8.5.1 For HCV-uninfected subjects

- Current health status will be reviewed and any changes since the last visit will be noted.
- All concomitant medications will be recorded (if prior to Day 90 visit). Immunosuppressant medications and medications for the treatment of HCV infection will be collected throughout the study as applicable.
- Approximately 23 mL of venous blood will be collected for hematology and biochemistry parameters, as described in Section 7.6.1.
- Approximately 100 mL of venous blood will be collected for immunologic assays.
- Approximately 20 mL of venous blood will be collected for anti-HCV, HbsAg, anti-HIV, and HCV viremia.
- A targeted physical examination may be performed, if indicated based on review of current health status.
- Information regarding adverse events will be collected (if before Day 90). All SAEs that have occurred since the last contact will be collected.
- Subjects will be thanked for participating in the study and contact information for end of study results will be confirmed.

8.5.2 For HCV-infected subjects

- Counseling and written information on acute hepatitis C treatment options will be provided along with a list of health care providers who are separate from this study; a referral to a community-based healthcare provider will be offered.
- Counseling on avoidance of HCV transmission, HIV infection, and pregnancy will be conducted.

- Referral to drug treatment and needle exchange programs will be provided.
- Current health status will be reviewed and any changes since the last visit will be noted.
- A targeted physical examination may be performed, if indicated, based on review of the current health status.
- Behavioral risk will be assessed using an interviewer administered questionnaire.
- SAEs that have occurred since the last contact will be collected.
- Approximately 138 mL of venous blood for hematology, biochemistry, HCV genotyping, anti-HCV, HCV quantitative viremia, and immunology will be collected.
- Approximately 5 mL of venous blood will be collected for HbsAg and anti-HIV for subjects who become HCV-infected prior to the 2nd dose of vaccine and choose to terminate early.
- Subjects will be thanked for participating in the study and contact information for end of study results will be confirmed.

8.6 Referral for Acute HCV Infection

All trial subjects with positive HCV RNA test results will be provided a referral to providers external to the study for evaluation for appropriate care and treatment of HCV infection. Treatment may include interferon alpha with or without ribavirin. Referrals will be provided at every visit at which a participant tests HCV RNA positive.

8.7 Subsequent Positivity for Anti-HCV: Distinguishing Intercurrent HCV Infection from Vaccine Induced Positive HCV Serology

It is expected that after vaccination some subjects may become positive for anti-HCV in the absence of infection as a result of exposure to antigens derived from HCV that are included in the vaccine. In the previous clinical trial, HCV001, seroconversion to HCV in absence of documented infection occurred only in 10% of vaccinated subjects. Anti-HCV testing will be done using a commercial enzyme immunoassay (EIA) on subjects who do not develop HCV infection during the trial. Following a positive EIA test, additional testing will be done to differentiate infection- from vaccine-induced antibodies (See Section 7.6). Testing will be conducted on stored blood samples obtained from monthly visits. Differentiation will be based on detection or not of antibodies to antigens not present in the vaccine. Subjects who develop vaccine induced anti-HCV will be informed at the end of the study and be provided with documentation explaining the reasons for their anti-HCV positivity for communication with their medical providers (with the subjects' consents). This will be discussed in detail at screening and in ICFs.

9 DMID Safety Reporting and Safety Assessment Monitoring

Regulatory requirements, including the FDA regulations and the ICH Guidelines for Good Clinical Practice, define safety monitoring and reporting responsibilities of sponsors and investigators to ensure the safety and protection of human subjects participating in clinical trials.

9.1 Responsibilities

Investigators participating in this clinical trial are responsible for and will:

- Evaluate subject safety including assessment of adverse events (AEs) for seriousness, severity, and causality
- Notify the sponsor (DMID) through their Pharmacovigilance contractor of SAEs immediately
- Provide detailed written reports promptly following immediate initial reports, including necessary documentation requested by the sponsor or IRB
- Inform the IRB of AEs as required by applicable regulatory requirements

9.2 Definitions

Adverse Event (AE)

An AE is any untoward medical occurrence in a clinical investigation subject who has received a study intervention and that does not necessarily have to have a causal relationship with the study product. An AE can, therefore, be any unfavorable and unintended sign (including an abnormal laboratory finding, for example), symptom, or disease temporally associated with the use of the study product, whether or not considered related to the study product.

Unexpected

An unexpected AE is an adverse reaction, the nature or severity of which is not consistent with the applicable product information (e.g., investigator's brochure [IB] for an unapproved investigational medicinal product). Unexpected refers to an experience that has not been previously observed. This includes events that are more serious than expected or occur more frequently than expected.

Expected

Any adverse experience, the nature, severity or frequency of which is consistent with the current IB; or with the risk information described in the investigational plan or protocol or consent form.

Serious Adverse Event (SAE)

An adverse event or suspected adverse reaction is considered "serious" if, in the view of either the investigator or sponsor, it results in any of the following outcomes:

- Death,
- A life-threatening adverse event*,
- Inpatient hospitalization or prolongation of existing hospitalization,
- A persistent or significant incapacity or substantial disruption of the ability to conduct normal life functions, or
- A congenital anomaly/birth defect.
- Important medical events that may not result in death, be life-threatening, or require hospitalizations may be considered serious when, based upon appropriate medical judgment, they may jeopardize the subject and may require medical or surgical intervention to prevent one of the outcomes listed in this definition. Examples of such medical events include allergic bronchospasm requiring intensive treatment in an emergency room or at home, blood dyscrasias or convulsions that do not result in subject hospitalization, or the development of drug dependency or drug abuse.
- * Life-threatening adverse event. An adverse event is considered "life-threatening" if, in the view of either the investigator or sponsor, its occurrence places the subject or subject at immediate risk of death. It does not include an adverse event, had it occurred in a more severe form, might have caused death.

9.3 Safety Reporting Requirements

9.3.1 Reporting Interval

All SAEs and new onset chronic illnesses will be documented from randomization through subject's last visit (Visit 26 or H09)/subject completion of all study assessments.

- New-onset chronic illnesses will be collected from randomization through a subject's last visit (Visit 26 or Visit H09). New-onset chronic illnesses are defined as any new ICD-10 diagnosis that is applied to the subject during the duration of the study, after receipt of the study agent, that is expected to continue for at least 6 months and requires continued health care intervention. To reference the International Statistical Classification of Diseases and Related Health Problems, 10th revision (ICD-10): http://www.cdc.gov/nchs/about/otheract/icd9/abticd10.htm
- Non-serious Adverse Events will be collected from randomization through 34 days post-vaccination 2 (approximately Day 90). All SAEs and AEs will be followed until they are resolved or determined by the PI to be medically stable,

even if this extends beyond the study-reporting period. Resolution of an adverse event is defined as the return to pre-treatment status or stabilization of the condition with the expectation that it will remain chronic.

At any time after completion of the study, if the investigator becomes aware of a serious adverse event that is suspected to be related to study product, the investigator will report the event to the DMID Pharmacovigilance contractor, DMID CROMS Pharmacovigilance Group.

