8.2.10 Days 150–270, Visits 11–15

Visit	Target (Day)	Window (Days)
11	150	+ 7
12	180	+ 7
13	210	+ 7
14	240	+ 7
15	270	+ 7

- Current health status will be reviewed and any changes since the last visit will be noted.
- A targeted physical examination may be performed, if indicated, based on review of current health status.
- Behavioral risk will be assessed using an interviewer administered questionnaire at visits 12 and 15.
- Approximately 100 mL of venous blood will be collected for immunologic assays at Visit 14.
- Immunosuppressant concomitant medications and medications for the treatment of HCV infection will be recorded.
- SAEs that have occurred since the last contact will be collected.
- Approximately 10 mL of venous blood will be collected for HCV viremia.
- Counseling on avoidance of HCV and HIV infection, and pregnancy will be conducted.
- Referral to drug treatment and needle exchange programs will be provided.

8.2.11 Day 300, Visit 16

(Window: Day 293 to 307)

- Current health status will be reviewed and any changes since the last visit will be noted.
- A targeted physical examination may be performed, if indicated, based on review of current health status.
- Immunosuppressant concomitant medications and medications for the treatment of HCV infection will be recorded.
- SAEs that have occurred since the last contact will be collected.
- Approximately 23 mL of venous blood will be collected for hematology and biochemistry parameters, as described in Section 7.6.1, and performed by the local laboratory.

- Approximately 10 mL of venous blood will be collected for HCV viremia.
- Counseling on avoidance of HCV and HIV infection, and pregnancy will be conducted.
- Referral to drug treatment and needle exchange programs will be provided.

8.2.12 Day 330, Visit 17

(Window: Day 323 to 337)

- Current health status will be reviewed and any changes since the last visit will be noted.
- A targeted physical examination may be performed, if indicated, based on review of current health status.
- Immunosuppressant concomitant medications and medications for the treatment of HCV infection will be recorded.
- SAEs that have occurred since the last contact will be collected.
- Approximately 10 mL of venous blood will be collected for HCV viremia.
- Counseling on avoidance of HCV and HIV infection, and pregnancy will be conducted.
- Referral to drug treatment and needle exchange programs will be provided.

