Biochemistry (mL)			14										14	14
Anti-HCV (mL)													5	5
HBsAg, anti-HIV (mL)													5	5
HCV Qualitative viremia (mL)	5	5	5	5	5	5	5	5	5	5	5	5	5	5
HCV Quantitative viremia (mL)	5	5	5	5	5	5	5	5	5	5	5	5	5	5
Anti-adenovirus Ab (mL)					10									
Immunology (mL)	100												100	100
Blood per visit (mL)	110	10	33	10	20	10	10	10	10	10	10	10	143	143
Cumulative blood volume (mL)	1077	1087	1120	1130	1150	1160	1170	1180	1190	1200	1210	1220	1363	

S, screening visit;

V, vaccination visit;

(X), if considered necessary, emphasizing any acute complaint;

A, only SAE's collected;

 B, All concomitant medications will be recorded through Day 90 (Day 30 if only receiving 1 vaccination).
 At visits after Day 90 (Day 30 if only receiving 1 vaccination), only immunosuppressants and medications for the treatment of HCV infection will be recorded;

C, windows dependent on Visit 6, Dose 2

D, Plasma saved from the blood collected for immunology assessments at this visit will be used for antiadenovirus Ab testing.

* Pregnancy test must be performed and documented as negative within 24 hours prior to each vaccination.

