4.5. Efficacy, Immunogenicity, and Safety Variables

See Section 3.3 for efficacy and immunogenicity variable definitions.

The safety variables to be assessed are reactogenicity events, unsolicited adverse events (AEs), serious adverse events (SAEs), and protocol specified clinical safety laboratory, physical exam, and vital sign parameters.

Subjects were to record temperature and the presence and intensity of post-vaccination reactogenicity events daily on an 8-day subject memory aid. Local solicited reactogenicity events include: pain, tenderness, erythema, induration and warmth at the injection site. Systemic solicited reactogenicity events include: fever, chills, arthralgia/joint pain, malaise/fatigue, myalgia/body aches, headache, nausea, vomiting, abdominal pain. Erythema and induration at the vaccination site will be measured in millimeters and functional grade. Any symptoms still present at Day 7 will continue to be followed until symptom resolution.

Solicited reactogenicity symptoms will be graded using the scale in section 9.4.4 of the protocol.

Unsolicited adverse event severity will be graded according to parameters shown in Appendix B of the protocol or if graded differently this will be noted in the tables using the definitions in section 9.4.2 of the protocol.

Clinical laboratory evaluations for safety will be performed by local (clinical) laboratories. Venous blood samples will be collected from each subject prior to each vaccination and according to the Study Schedule in Appendix C of the protocol. Clinical safety lab parameters to be followed include WBC, HgB, platelets, ALT, and creatinine. Urine will be collected to evaluate glucose and protein, which will be performed at screening only. Toxicity grades for each clinical laboratory parameter can be found in Appendix B of the protocol.

Multiple observations within a specific visit period are accepted. In the case of multiple observations within a specific window, the assessment value that is closest to the scheduled visit will be used in the analyses for the post-baseline records. For screening and baseline visits, the last assessment value prior to first vaccination will be used as the baseline measurement. All the recorded data will be listed. If observations have the same distance to the scheduled assessment, the latest one will be used.

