6.3.3. According to Protocol Population

The according to protocol (ATP) population is a subset of the mITT analysis cohort, excluding subjects with major protocol deviations that would compromise the assessment of vaccine efficacy (see list below). Subjects who meet any of the criteria listed below will be censored in time to event analyses according to the date of first occurrence of the criteria, and will be excluded from all other types of analyses. The ATP cohort will exclude subjects who:

- a. receive treatment for acute HCV infection;
- b. were enrolled but subsequently found to have been ineligible at enrollment based on a criterion that could reasonably be expected to affect vaccine efficacy (as reviewed by the blinded clinical review team [see below]);
- c. did not receive both doses of vaccine or control;
- d. acquired HCV infection prior to receipt of the second vaccination;
- e. received the wrong (non-randomized) product at either dose;
- f. received the second dose fewer than 42 days or more than 70 days after the first dose;
- g. received an immunosuppressant other than inhaled or topical steroids;
- h. were immunized against another pathogen or received immunoglobulins or other blood products within 14 days of either dose of study vaccine;
- i. have autoimmune disease; and
- j. have a confirmed or suspected immunosuppressive or immunodeficient state.

Membership in the ATP efficacy cohort will be assessed by a centralized, blinded, clinical review team comprised of the site PIs and the sponsor prior to unblinding of the study data.

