9.3.2. Unsolicited Adverse Events

Adverse events will be collected through day 90. At visits following Day 90, only SAE's will be collected. Adverse events will be graded on a scale of 0 (none), 1 (mild), 2 (moderate), 3 (severe), 4 (life threatening), and 5 (death).

Adverse events will be coded to a Medical Dictionary for Regulatory Activities Terminology (MedDRA) version 20.1 or later. Verbatim description, the MedDRA System Organ Class, and Preferred Term for all adverse events will be contained in the subject data listings.

The proportion of subjects reporting at least one unsolicited adverse event will be summarized by dose and over all doses, MedDRA® system organ class (SOC) and preferred term (PT) for all subjects and each actual treatment group. Denominators for percentages are the number of subjects who received the dose being summarized. A 95% Blaker CI will be presented for each SOC and PT. (Table 58, Table 59, Table 60)

Adverse events by subject will be presented in Listing 11.

The following summaries for unsolicited adverse events will be presented by SOC, PT, dose and treatment group:

- Number and percentage of subjects by dose, HCV Infection Status, maximum severity and maximum relationship to study product including Frequency (Event level) of events for all subjects and by actual treatment received ([Table 61](#), [Table 62](#), [Table 63](#), [Table 64](#), [Table 65](#), [Table 66](#));
- Number and percentage of subjects by dose, HCV Infection Status, maximum severity and maximum relationship to study product including Frequency (Event level) of events for all subjects and by actual treatment received ([Table 67](#), [Table 68](#), [Table 69](#));
- Subject incidence and total frequency of adverse events over time (Days 1-8, Days 8-55, Days 56-63, Days 64-90) ([Table 70](#), [Table 71](#), [Table 72](#));
- Subject listing of non-serious adverse events of moderate or greater severity ([Table 73](#));
- Bar chart of total frequency of adverse events by severity and SOC ([Figure 27](#));
- Bar chart of subject incidence of adverse events by severity and SOC ([Figure 28](#));
- Bar chart of total frequency of adverse events by relationship to study product and SOC ([Figure 29](#));
- Bar chart of subject incidence of adverse events by relationship to study product and SOC ([Figure 30](#));

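### Protocol 9.3.1 collects new-onset chronic illness to the last visit, but the visit charts and SAP limit event collection after about Day 90 to SAEs, and no by-arm output is planned

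*Protocol*

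**What the plan says.** Protocol 9.3.1 sets three collection periods. SAEs run to the last visit. Non-serious AEs stop 34 days after dose 2, about Day 90. The third category has its own bullet: "New-onset chronic illnesses will be collected from randomization through a" subject's last visit, Visit 26 or H09. It is a new ICD-10 diagnosis made after receipt of study agent "that is expected to continue for at least 6 months and requires continued health care intervention". Nothing in that definition requires the event to be serious.

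The operational text differs:

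- Protocol 8.2.10, in wording repeated from Day 120 to Day 600 and at H01–H09: "SAEs that have occurred since the last contact will be collected". Chronic illness is not named.
- Protocol 8.5.1 (early termination, uninfected): AEs if before Day 90, then SAEs. Section 8.5.2 (infected) names SAEs.
- Protocol Appendix C, footnote A on the AE/SAE row for Visits 10–26: "only SAE's collected". Appendix D footnote F gives the same limit after Day 90.
- SAP 9.3.2: "At visits following Day 90, only SAE's will be collected".
- SAP 4.5 begins its list with "The safety variables to be assessed are reactogenicity events, unsolicited adverse events (AEs), serious adverse events (SAEs") and continues with laboratory, examination and vital-sign parameters. Chronic illness is absent there and from the lists of tables and listings.

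SAP Section 14 records departures from the protocol and does not mention this one.

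**The concern.** The two sets of instructions cannot both be followed for a non-serious chronic diagnosis made after Day 90. A site using 9.3.1 reports it; a site using the charts does not. Monthly visits are normally run from the charts, so the conflict matters in practice.

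What is at stake is the description of delayed, non-serious clinical harm. Protocol 11.1 makes detection of safety problems a main purpose of the study. Protocol 2.3 says no clinical data exist for AdCh3NSmut1, although Section 2.2.3 describes its predecessor as nearly the same and 38 volunteers received that vector in HCV001. An autoimmune or thyroid diagnosis at Day 200, handled as an outpatient and not meeting an SAE criterion, is the kind of event the chronic-illness category exists to catch. If sites differ in what they record, and nothing is tabulated by arm, the final report cannot say whether such diagnoses were balanced.

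The definition can also be met by chronic HCV infection, which is the efficacy endpoint. The documents do not say how to keep the two apart.

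**Working it through.** **Is it a contradiction or only an omission?** Protocol 9.2 defines an AE broadly enough to include any new diagnosis, so a non-serious chronic illness is a non-serious AE. A rule that only SAEs are collected after Day 90 excludes it, while 9.3.1 includes it. The two footnotes and SAP 9.3.2 therefore conflict with 9.3.1. The visit lists, which name SAEs without the word only, merely omit it.

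**Do other entries fill the gap?**

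- Health status is reviewed and changes are noted at each later visit, but no instruction turns a noted diagnosis into a reported event.
- Medical history at follow-up is as needed, and the chart legend stresses acute complaints.
- Concomitant medication after Day 90 is limited to immunosuppressants and HCV treatment, so most new long-term therapy would not reveal a diagnosis.
- Protocol 8.4 refers AEs back to Section 9.3, but only for unscheduled visits.
- SAP Listing 7 allows an onset during the study, but it lists pre-existing conditions.

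**How long is the affected period?** The protocol uses 30-day months. Its own follow-up figures reproduce: 600/30 = 20 months for uninfected subjects, and (600 + 270)/30 = 29 months for a subject first positive at Day 600.

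- Uninfected completers: 600 − 90 = 510 days; 510/30 = 17.0 months; 510/600 = 85%. This spans 17 scheduled visits (Visits 10–26).
- With visit windows: (593 − 97)/30 = 16.5 to (607 − 83)/30 = 17.5 months.
- Infected subjects who complete H09, first positive on day x: exit at x + 270, affected period x + 270 − 90 = x + 180 days.

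| First positive (day) | Exit (day) | Affected period (months) | Total (months) |
|---|---|---|---|
| 30 | 300 | 7 | 10 |
| 300 | 570 | 16 | 19 |
| 600 | 870 | 26 | 29 |

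The documents give no expected number of chronic illnesses, so the count affected cannot be calculated.

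**The case against.** The strongest reply is that 9.3.1 binds sites by itself. The footnotes sit on the AE/SAE row and can be read as repeating the split 9.3.1 makes between serious and non-serious AEs, leaving its separate chronic-illness bullet intact. The eCRFs and manual of procedures are not available here and may carry the item. This stands against any claim about what was captured. A reader might infer that these illnesses are lost after Day 90; the documents show contradictory instructions, not loss. The reply does not explain why neither chart has a chronic-illness row, and it leaves the missing SAP output untouched.

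A reader might also infer that this is the only planned look at delayed non-serious harm. It is not. Safety laboratories are drawn at Days 120, 300 and 600 and at every H visit and are tabulated by arm, and immunosuppressants are recorded throughout. Some outpatient diagnoses would also be SAEs, because the definition covers incapacity and important medical events. The gap is confined to non-serious clinical diagnoses.

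A third tempting inference concerns the primary analysis. ATP exclusions include subjects who "have autoimmune disease" or an immunodeficient state, with censoring at first occurrence, so one might conclude that after Day 90 this date exists only for SAEs. The documents do not support that. Immunosuppressant use is recorded to the end and is its own criterion, HIV is tested at the last visit, sites have access to medical records, and a blinded clinical team decides ATP membership.

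**Conclusion.** The conflict is real and should be resolved. Protocol 9.3.1 requires collection to Visit 26 or H09; two chart footnotes and SAP 9.3.2 exclude non-serious events after about Day 90. Separately, and whichever rule sites follow, the SAP plans no by-arm report of chronic illness and does not declare the omission.

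The affected period is about 17 of 20 months for uninfected completers only. It should not be read as one figure for everyone: infected completers range from about 7 of 10 to 26 of 29 months, and early dropouts have less. These figures assume Day 90 as the end of non-serious AE collection and 30-day months.

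The three primary safety endpoints do not include chronic illness and are unaffected. No change to the ATP efficacy estimate is shown. The consequence is a weaker longer-term safety description, of a size the documents do not allow one to state.

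**What to change.** Reconcile the passages to 9.3.1:

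- Add 'and new-onset chronic illnesses' to the post-Day-90 SAE item in Protocol 8.2.9–8.2.15, 8.3 and 8.5, to Appendix C footnote A and Appendix D footnote F, and to SAP 4.5 and 9.3.2.
- Add to the SAP one table and one listing by treatment group in the safety population, by MedDRA system organ class and preferred term, with onset day. Report HCV infection separately, because it is the efficacy endpoint.
- The SAP refers to reviews held in October 2016, so many visits will have passed. For those, list the chronic illnesses found in source records and state in the study report that earlier collection followed conflicting instructions. A new form item cannot recover those visits.

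The cost is wording, one form item at visits already scheduled, one table and one listing. No visit or procedure is added.
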